Liverpool Centre for Cardiovascular Science

The FISH&CHIPS Protocol

FFRCT In Stable Heart disease and Coronary Computed Tomography Angiography Helps Improve Patient care and Societal costs

Study Objective	The primary objective of FISH and CHIPS is to identify differences in health- related events, time to diagnosis and overall healthcare costs of a stable chest pain population undergoing Coronary Computed Tomography Angiography (CCTA) and Fractional Flow Reserve (FFR _{CT}), compared to a previous 'standard of care' diagnostic chest pain pathway of CCTA and non- invasive functional testing.	
Study Design	This is a multi-centre, retrospective, observational analytic cohort study design. The study will utilise the electronic health record (EHR) data already collected by NHS England on all patients that underwent a CCTA for the assessment of coronary artery disease over a 2-year period (April 2017-April 2019). All patients were treated in accordance with the latest NICE clinical guidance (CG 95 2016). Healthcare data will be collected from 6 months prior to and 12 months following the index CCTA. Hospital admissions data collected will include inpatient hospital admissions, outpatient visits, cardiovascular diagnostic tests and procedures. All subsequent clinical events including myocardial infarction and all-cause death will be measured as clinical outcomes. Costs are determined from the NHS national tariff system.	
Study Principal	[name]	
Investigator	Liverpool Heart and Chest Hospital and the University of Liverpool,	
	[name],	
	Liverpool,	
	[name]	
	United Kingdom	
Sponsor	Liverpool Heart and Chest Hospital,	
	[name],	
	Liverpool,	
	[name]	
	United Kingdom	
FISH	& CHIPS MRC Medical Research Council	

RESEARCH REFERENCE NUMBERS

IRAS Number:	285996
ISRCTN Number / Clinical trials.gov Number:	
FUNDERS Number:	MR/T024933/1

Medical MRC

Investigator Protocol Signature Page

The undersigned confirm that the following protocol has been agreed and accepted and that the Chief Investigator agrees to conduct the trial in compliance with the approved protocol and will adhere to the principles outlined in the Medicines for Human Use (Clinical Trials) Regulations 2004 (SI 2004/1031), amended regulations (SI 2006/1928) and any subsequent amendments of the clinical trial regulations, GCP guidelines, the Sponsor's (and any other relevant) SOPs, and other regulatory requirements as amended.

3.1 Professional Summary

Protocol Title	FFRCT In Stable Heart disease & CCTA Helps
	Improve Patient care and Spending
Investigation strategy	CCTA plus FFRCT reduces healthcare resource
	utilization and costs compared to a CCTA
	strategy alone.
Study Principal Investigator	[name]
Academic Research Organization	Liverpool Centre for Cardiovascular Science
	(LCCS), Liverpool Heart and Chest Hospital,
•	Liverpool, UK
Sponsor	The University of Liverpool
Participants and Study sites	Approximately 100,000 patients from 25 sites
	who received a CCTA for the assessment of CAD
	in NHS England.
Study Planned Duration	36 months
Primary study objective	To determine whether a CCTA and FFRCT
	diagnostic pathway reduces health-related
	events, time to diagnosis and overall healthcare
	costs compared to a 'standard of care' CCTA
	diagnostic chest pain pathway.
Primary hypothesis	The addition of FFRCT into a CCTA diagnostic
	pathway will be safe with no difference in major
	adverse cardiovascular event rates or death
	whilst reducing the time to diagnosis, result in
	fewer downstream tests and reduce overall costs
	to the healthcare system.
Population	Chest pain patients with suspected stable
	coronary artery disease being clinically
	investigated with a CCTA in England.
Study Design and Methods	A pragmatic 'real world' multi-centre,
	retrospective, observational analytic cohort
	study design. All patients receiving a CCTA at
	institutions utilising FFRCT as part of NHS
	England's Innovation and Technology Payment
	(ITP) programme. Participants will be recruited
	from 1 year pre-ITP and the 2 years of the ITP
	programme. Patients will be followed up at a
	minimum of 24-months post CCTA for the pre-
Duine and Findle sint	defined primary and secondary endpoints.
Primary Endpoint	Primary and secondary outcomes measured:
	1. MI event rate, hospitalization for
	acute coronary syndrome, MI deaths
	and all-cause death.
	2. Downstream testing: numbers of

MRC Researc

	 non-invasive functional tests, and invasive coronary angiograms without revascularisation performed following the index FFRCT. 3. Cost analysis: Total cost to the NHS of the index test and all downstream investigations and hospital admissions. 	
Secondary Endpoint	 Time to diagnosis- Trust Referral to Treatment (RTT) time. 	
	 Qualitative assessment of the impact of the FFRCT health technology 	
Study follow up	Participants will be followed up to a minimum of 24 months	

3.2 Plain English Summary

Chest pain may be a symptom that is related to a narrowing of the heart blood vessels (coronary artery disease [CAD]). This chest pain, known as angina, can result in a reduced quality of life and, if not diagnosed and managed appropriately, could result in a heart attack. Coronary disease remains the largest cause of death in the United Kingdom today, with one death every 4 minutes. Guidelines recommend the use of tests to help diagnose and manage chest pain 'angina' patients. Coronary computed tomography angiography (CCTA) is a test that takes images of the heart blood vessels. It is the main test for patients presenting with angina, as it is excellent at saying when the heart blood vessels are normal and can be reassuring for patients. However, when narrowing's are present CCTA lacks the ability to tell whether they are causing the patient's symptoms.

A new technology, CT-derived fractional flow reserve (FFRCT) uses the CCTA images to make a 3D model of the heart blood vessels that shows whether there is a limitation in the blood flow to the heart which is causing the symptoms. The National Institute for Health and Care Excellence (NICE) recommends the use of FFRCT in a chest pain pathway. However, use of this new technology remains limited due to funding restrictions and uncertainty as to its benefit in the NHS.

This study aims to determine the extent to which the new FFRCT technology is safe and reliable, provides a quicker time to diagnosis for the patient, reduces the need for further tests and thus does the investment in the test represent good value to the NHS.

MRC

4 Introduction

4.1 Background

The investigation of suspected stable coronary artery disease (CAD) should primarily be based on a non-invasive strategy (Knuuti *et al.*, 2020). In the United Kingdom Coronary Computed Tomography Angiography (CCTA) is now recommended as the first-line diagnostic test for patients with suspected angina and no prior CAD. (NICE, 2010) This recommendation by the National Institute for Health and Care Excellence (NICE) in 2016 was primarily driven by the very high sensitivity of CCTA to detect the presence or absence of coronary atheroma. (Nielsen et al., 2014; Meijboom et al., 2008) Given that the majority of patients with suspected angina turn out to have non-cardiac chest pain, and the majority of CCTA scans performed for this purpose show only minimal or no CAD, a significant proportion of patients can be immediately reassured by CCTA in the current NICE guidelines pathway. (Fordyce, Newby, & Douglas, 2016) However, in approximately a third of cases, CAD detected by CCTA is either indeterminate due to dense calcification or of intermediate severity which results in only modest specificity of CCTA to detect functionally significant 'ischaemic' CAD - and this remains its Achilles' heel. (Meijboom et al., 2008)

Recent advances in technology allow the use of raw CCTA images with computational fluid dynamic modelling to produce a 3D haemodynamic representation of the coronary tree flow limitation. (Lee et al., 2018) (Conte et al., 2017) (Taylor, Fonte, Min, City, & Angeles, 2013) This CT-Derived Fractional Flow Reserve (FFRCT) has developed rapidly since first concept and is now used in routine clinical practice. NICE, in a medical technology guidance (MTG 32), stated 'the clinical and cost effectiveness evidence justified FFRCT's use as a second line functional test for indeterminate or intermediate coronary stenoses'. The guidance also commented that 'based on the current evidence, using HeartFlow FFRCT may lead to cost savings of £214 per patient. By adopting this technology the NHS in England may save a minimum of £9.1 million by 2022 through avoiding invasive investigation and treatment'.

4.2 Study Rationale

The accurate diagnosis of CAD is important to allow the appropriate medical treatment and post-test risk stratification to identify patients that might benefit from revascularisation. FFR_{CT} is a noninvasive physiological test that can assess flow limitation across a coronary stenosis with high diagnostic accuracy and good correlation to invasive FFR.(Nørgaard *et al.*, 2017) FFR_{CT} has been shown in trials to reduce the total number of inappropriate invasive coronary angiograms (ICAs) post-CCTA, by reducing the number of cases with no obstructive coronary artery disease. This increases the revascularization treatment rate, which represents a more efficient use of the expensive catheter angiography laboratory.(Douglas *et al.*, 2015)[,] (Jensen *et al.*, 2017)[,] (Nørgaard *et al.*, 2014) Patients could therefore be receiving the test with the highest accuracy, improving diagnostic certainty, thereby reducing unnecessary downstream tests and the time to treatment.

FISH&CHIPS

The NHS should benefit by reducing the number of invasive tests and the wider economy will benefit from fewer lost working days. In addition, the ITP has allowed national coverage of FFR_{CT} which has the potential to remove regional variations in clinical practice and spending costs.

The existing evidence for the use of FFRCT is based on randomised controlled trials, registry studies and economic analysis from a US providers' perspective. There is no real-world comparative data, and no literature from the perspective of NHS practice, which differs from the more 'invasive' approach in the US. This research will answer whether an NHS FFRCT pathway is better for the patients in terms of safety, reducing unnecessary alternative tests and time to treatment compared to previous 'standard of care' diagnostic pathways (including CCTA alone, stress echocardiography, stress perfusion MRI and nuclear scintingraphy). The impact on the NHS will be determined by comparing costs of a CCTA and selective FFRCT pathway to those of a standard of care pathway as well as the number of hospital visits.

5 Study Objectives

5.1 Primary objective

The study aims to identify differences in health-related events, time to diagnosis and overall costs in a clinical population undergoing CCTA and FFR_{CT} for symptoms suggestive of stable CAD, compared to a previous 'standard of care' diagnostic chest pain pathway.

5.2 Secondary objective

5.3 Primary Endpoints:

1. Safety: Has the implementation of FFR_{CT} been safe?

End points: Myocardial infarction event rate, hospitalization for acute coronary syndromes and mortality (all-cause and cardiovascular).

2. Time to Diagnosis: Does FFR_{CT} reduce the time to diagnosis and treatment?

End points: Trust Referral to Treatment (RTT) time.

3. Downstream testing: Does FFR_{CT} reduce the number of downstream investigations and the number of overall invasive and non-invasive diagnostic tests?

End points: numbers of non-invasive functional tests, and invasive coronary angiograms without revascularisation performed following the index FFR_{CT} .

4. Cost analysis: Does the technology represent value for money?

End point: Total cost to the NHS of the index test, all downstream investigations, hospital admissions and outpatient visits.

5.4 Exploratory Endpoints:

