7.1 Setting and Target Population

The study population will include all patients that received a CCTA for symptoms suggestive of CAD at a participating institute, 12 months prior to the institutes first FFRCT study and up to 24 months

MRC

 $\mathcal{L}_{\mathcal{L}}$

FISH&CHIPS

following (total study period up to 36 months). The timeframe of study recruitment is dependent upon the starting time of each centre in the ITP programme. Centres that had a later start date (onboarding) will have a shorter recruitment period, with a minimum of 12 months. These centres represent the 'real-world' NHS hospitals that are a mixture of secondary and tertiary referral centres (not dedicated academic or research sites) with clinical experience in CCTA who have met the minimum quality standards set out by NHS England. Thus, the study population represents a true reflection of the current CCTA practice in the national population, reducing the potential effect of selection bias seen in many RCT's.

A study population of 85,292 patients received either CCTA analysis alone (standard of care group, n=75,361) or CCTA and Heartflow FFRCT analysis (FFRCT group, n=9,799) during the two years of the new technology being available to each site. The total study population over the 36 months is likely to be over 100,000.

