8.2 Statistical Analysis

Analysis of the primary end-point is based on the rate of adverse events (MACE) as a composite of all-cause death, myocardial infarction and invasive coronary angiography without revascularization. Event rates over time will be calculated using Kaplan-Meier methodology from the time of the CCTA. Cox proportional hazard ratios will be used to determine the odds ratio (OR) of receiving revascularization post FFRCT compared to other tests.

Time to diagnosis will be compared using an 'intention to diagnose analysis' by analysing groups according to their investigative test (FFRCT vs CCTA alone).

The primary cost analysis will include total patient pathway costs at 12 months, with comparison between the two testing strategies. The mean cost difference with 95% confidence intervals and P value will be calculated. Sub-analysis will categorise the total costs breakdown as; Investigations, hospital stay, procedural costs.

Cost sensitivity analyses will be applied to the modelling, looking at different cost utilities in the UK and regional variability.

9 Good Clinical Practice

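### The downstream-test count starts at an FFRCT that comparator patients never had, and it omits tests that its own question asks about

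*Protocol*

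**What the plan says.** Protocol 5.3 item 3 makes downstream testing a primary endpoint. The question is whether FFRCT can "reduce the number of downstream investigations and the number of overall invasive and non-invasive diagnostic tests". The endpoint given to answer it is a count of functional tests and of "invasive coronary angiograms without revascularisation performed following the index" FFRCT. Section 3.1 repeats the rule: "invasive coronary angiograms without revascularisation performed following the index FFRCT". Neither place states how long the count runs.

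The groups in 7.1 are "CCTA analysis alone (standard of care group, n=75,361) or CCTA and Heartflow FFRCT analysis (FFRCT group, n=9,799"). Sections 3.1, 6 and 7.1 add the patients scanned in the 12 months before each site's programme began, and 5.1 names a previous standard-of-care pathway as the comparator.

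Elsewhere time runs from the CCTA. The synopsis collects data around the index CCTA, 7.4 follows patients from the CCTA, and 8.2 states: "Event rates over time will be calculated using Kaplan-Meier methodology from the time of the CCTA".

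**The concern.** There are two separate defects in one primary endpoint.

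The first is the starting point. A count that begins at the index FFRCT has no beginning for a patient who never had one. An analyst must then supply a start date for the comparator. The natural choice is the CCTA, which gives the two groups different origins. A stress test or angiogram done after the CCTA but before the FFRCT would count for a comparator patient and be lost for an FFRCT patient.

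The second is scope. The question concerns the overall number of tests, but the endpoint covers only some of them. FFRCT is not counted, although 4.1 cites national guidance that places it as a functional test used after CCTA, the role filled by the tests that are counted. Angiograms that lead to revascularisation are not counted either. A patient whose stress test is replaced by an FFRCT scores as having one test fewer, when the number of tests after CCTA is the same.

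At stake is whether a reported reduction in this endpoint can be read as fewer tests performed. As defined, it cannot.

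**Working it through.** The protocol gives no expected test count, effect size or power for this endpoint, so there is no figure to reproduce. The check compares the stated rules and then uses an accounting identity.

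**Time origin**

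- Downstream tests (3.1, 5.3 item 3): from the index FFRCT.
- Data window (synopsis): 6 months before to 12 months after the index CCTA.
- Follow-up (7.4): at least 24 months after the CCTA.
- Event rates (8.2): from the CCTA. The composite there includes invasive angiography without revascularisation, so the same event has one origin in 8.2 and another in 5.3.

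The number of tests lost between CCTA and FFRCT cannot be estimated, because the protocol gives neither the interval nor the number of tests in it.

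**Scope**

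Per patient, let f be functional tests other than FFRCT, X be FFRCTs, A be angiograms with revascularisation and N be angiograms without. All are counted from the CCTA.

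- Endpoint: E = f + N
- Total: T = f + X + A + N
- FFRCT group minus CCTA-alone group, with X = 1 and X = 0: difference in T = difference in E + 1 + (A_F − A_C)

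*FFRCT term.* Assume equal angiogram rates and 0.05 other functional tests per FFRCT patient. None of these rates is in the protocol.

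| Functional tests per comparator patient (assumed) | Difference in E | Difference in T |
|---|---|---|
| 0.1 | 0.05 − 0.1 = −0.05 | +0.95 |
| 0.3 | 0.05 − 0.3 = −0.25 | +0.75 |
| 0.5 | 0.05 − 0.5 = −0.45 | +0.55 |
| 1.0 | 0.05 − 1.0 = −0.95 | +0.05 |

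The sign changes in every row, but largely because T gives every FFRCT patient at least one test. A total count is therefore not fair between these two groups. It is fair per CCTA patient across whole pathways. From 7.1, 75,361 + 9,799 = 85,160, and 9,799/85,160 = 0.115. (The stated total of 85,292 gives the same 0.115.) With one FFRCT per FFRCT patient, leaving FFRCT out lowers the programme-period mean by 0.115 tests per CCTA patient. A true fall in total testing needs f + A + N to fall by more than that.

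*Angiogram term.* Its contribution to the difference in E is −(A_F − A_C). Rates are again assumed.

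| Angiograms per patient, FFRCT v comparator | Share revascularised | A_F v A_C | Shift from omitting A |
|---|---|---|---|
| 0.30 v 0.30 | 70% v 50% | 0.21 v 0.15 | −0.06 (towards FFRCT) |
| 0.24 v 0.30 | 62.5% v 50% | 0.15 v 0.15 | 0 |
| 0.20 v 0.30 | 50% v 50% | 0.10 v 0.15 | +0.05 (against FFRCT) |

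If the number of angiograms is held at 100 and the share revascularised goes from 50% to 65%, the counted angiograms go from 50 to 35. That is a 30% fall with no angiogram avoided (10% at a share of 55%, 40% at 70%). This shows only that the count can move without a change in angiography.

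**The case against.** The best defence is that both exclusions are deliberate. Section 4.2 aims at unnecessary testing, and an angiogram that ends in revascularisation is not what the investigators want to avoid. FFRCT is the technology under evaluation, is computed from images already taken, and is absent from the downstream tests listed in section 6. The intended origin can also be recovered from 7.4 and 8.2. Much of this stands: functional tests plus angiograms without revascularisation is a sound measure of unnecessary downstream testing and should be kept. It does not rescue the claim about overall tests, and an origin repeated in two places still has to be corrected.

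A reader might go further and infer that the definition favours FFRCT by construction. The documents do not support that. The angiogram omission can act in either direction. Section 4.2 does say "This increases the revascularization treatment rate", but as a result of avoiding inappropriate angiograms, so holding their number fixed sets aside the mechanism the protocol describes. FFRCT is used selectively, while 8.1 expects 37% normal and 38% non-obstructive scans among CCTA patients. Such patients plausibly need few further tests and lower the CCTA-alone count. The net direction is therefore open.

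A reader might also infer that the gap carries into the cost result. It does not: 5.3 item 4 defines cost separately and includes the index test and all downstream investigations.

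**Conclusion.** The point holds in two parts.

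1. The stated origin is wrong for a comparative endpoint. The count is undefined for CCTA-alone and pre-programme patients, or starts at different times in the two groups, and it conflicts with the CCTA origin in the synopsis, 7.4 and 8.2. This rests on the text alone. Its numerical effect is unknown.
2. The endpoint does not answer the overall-tests question set in 5.3. The omitted FFRCTs amount to 0.115 tests per CCTA patient in the programme years, assuming one per FFRCT patient. The angiogram omission has no fixed sign.

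That each of the 9,799 FFRCTs replaces a functional test, and that counted angiograms fall by 30%, are illustrations under assumed rates and not estimates of bias.

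**What to change.** In 3.1 and 5.3 item 3, count from the index CCTA date over one fixed window, the same in all groups, and state its length. The synopsis window of 12 months and the 24-month minimum in 7.4 are the candidates already in the protocol.

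Keep functional tests plus angiograms without revascularisation as the measure of downstream or unnecessary testing. Add a total count of functional tests, FFRCT and all invasive angiograms per CCTA patient, with angiograms split by whether revascularisation followed. Compare the total between whole pathways (pre-programme versus programme period), not between FFRCT and CCTA-alone patients.

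The data sources are already planned in section 6, so the cost is rewording and slightly more analysis. Any reduction may look smaller on the total count.

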5.4.1 Qualitative Assessment

A qualitative survey of clinicians at the NHS trusts implementing a FFRCT pathway will be performed to assess the impact of a change in the service aligned with FFRCT. Factors assessed will include: ease of implementation (governance and IT), user friendliness, ease of clinical integration and practicality.

5.4.2 Imaging biomarkers

Using the list of CCTA originally provided by the sites, the participating centres PACS teams will send the anonymised CCTA datasets to the CTU data storage for future linkage to the outcome data provided by NHS Digital. This process will ensure that anonymity is preserved while providing for a valuable resource in terms of a large database of anonymised imaging datasets with outcome data. There will also be the opportunity to repeat the data capture from NHS Digital in future years to establish medium and long-term outcomes. The purpose of creating this repository of anonymised outcome and imaging data is to allow for future research projects into image analysis of CTA including deep learning algorithms, radiomics analysis, and biomechanical modelling of coronary arteries all with the goal to improving future risk stratification to better target therapeutic interventions.

6 Study Design

This is a multi-centre, retrospective, observational analytic cohort study design.

This pragmatic 'real-world' trial, is designed to utilise big data to answer practical health questions and determine clinical outcomes in a timely fashion. Randomized clinical trials (RCT's) in comparative effectiveness research (CER) have been considered the gold standard. These are however, subject to several problems, including cost, patient selection bias and slow translation of knowledge into practice. (Angus, 2015) This study design removes any patient treatment heterogeneity effect seen in RCT's by assessing the impact of a new intervention on a whole population. (Longford, 1999) by utilising the electronic health record (EHR) data already collected by the NHS. This trial will thus represent a true assessment of the effectiveness of a new health technology on a population basis in the current NHS system and will enable the rapid translation of research into clinical and health care policy decisions.

Participants will include all individuals who had a CCTA performed at an institute participating in the NHSE FFRCT ITP during 2018-2020. All CCTA 12 months prior to and up to 24 months following the

FISH&CHIPS

Medical Research Council

start of a FFRCT programme (total study period 36 months) will be assessed. The cohort from this population that received an FFRCT will be separately identified, with linkage to the NHS digital data outcomes. HeartFlow will provide FFRCT-specific data.

NHS Digital's Data Access Request Service (DARS) will be queried to provide the patient episodes over the study period. NHSD collects national data sets containing details of all admissions, accident and emergency (A&E) attendances, and outpatient appointments at NHS hospitals in England. DARS will extract data from the following data sets:

- Emergency Care Data Set (ECDS)
- Hospital Episode Statistics Admitted Patient Care (HES APC)
- Hospital Episode Statistics Critical Care (HES CC)
- Hospital Episode Statistics Outpatients (HES OPC)
- Hospital Episode Statistics Accident and Emergency (HES AE)
- Diagnostic Imaging Dataset (DID)
- Medicines Dispensed in Primary Care Data Set (from NHS Business Authority)
- Civil Registration Deaths

These data sets will provide the following information:

- Patient demographics (such as age group, gender and ethnicity)
- Administrative information (such as dates and methods of admission and discharge)
- Geographical information; such as where patients are treated and the area where they live (post code).
- Medications (type, dose and whether processed)
- ICA and revascularisation data linked to patients.
- Incidence of downstream testing; stress echocardiograms, stress MRI or nuclear scintigraphy.

Costs will be calculated for all hospital attendances, diagnostic investigations and treatments from the published NHS England National Prices and Tariff workbook (2017-2019- HRG/OPEC codes) with the appropriate market forces factor applied. Health economic modelling will be performed by the University of Liverpool.

Referral to treatment (RTT) data is collected by each NHS trust for each patient. This data will be collected by the local research teams.

7 Study Population

